11.1 Adverse events

All assessments will be done for all patients, part I and part II separately.

Adverse events (AE) will be coded using the MedDRA® dictionary. The current version will be used at time of database lock and presented by primary System Organ Class (SOC) and Preferred Term.

The analysis will focus on the treatment-emergent AEs (TEAEs). When an AE occurs after written consent has been obtained but before the first dose of study drug, the AE will be considered a non-treatment emergent AE. An AE that occurs (or worsened) on or after the time the patient receives his/her first dose of study drug (until his/her last study visit) will be considered a treatment emergent AE (TEAE). See also CSP section 14.6.2 for definition of non-treatment adverse events.

Please note the definition of study periods and adverse event reporting periods in section 5.5 above. Please also note that analyses for TEAE will be based on the safety population (SAF). Overview tables including non-TEAEs will be based on the APE to also include patients not treated in the study.

For the analysis of TEAEs only those TEAEs are taken into consideration which are reported from first treatment to the safety visit after treatment (independent of the planned duration between treatment start and Day 49 safety visit). For part I this is the duration between PK treatment and the Day 49 PK safety visit or earlier (if a bleeding event happened before Day 49 PK safety visit), and for part II this is for each bleeding event the duration between treatment of the bleeding event and Day 49 safety visit or earlier (if another bleeding event happened before Day 49 safety visit).

All other TEAEs reported out of these time frames will be counted and listed. Exception is the analysis of related serious adverse events (related SAEs) which are included in the analysis irrespective of the onset time after first administration of IMP:

If 'Day 49 safety visit' is not done, the period for inclusion of TEAEs in the analysis is from baseline (treatment start) to 49 days post-baseline.

The total number and percentage of patients reporting at least one AE and the absolute count of AEs will be tabulated for each age group and overall. This initial summary will be based on the APE set and provide a breakdown of the following:

- Any AE
- Any non-severe AE
- Any TEAE
- Any non-serious TEAE
- Any non-severe TEAE
- Any treatment-related TEAE
- Any severe AE

- Any severe TEAE
- Any severe treatment-related TEAE
- Any SAE
- Any serious TEAE
- Any serious treatment-related TEAE
- Any AE leading to discontinuation from study
- Any TEAE leading to discontinuation from study
- Any treatment-related TEAE leading to discontinuation from study
- Any AE with outcome of death
- Any death
- Any pregnancy

In the SAF number and frequencies (i.e. percentages) of patients with TEAEs will be given by System Organ Class (SOC) and by Preferred term within each SOC (total, for each age group) together with the number of events for the following:

1. All TEAEs
2. Serious TEAEs
3. All TEAEs considered related (see details below)
4. Serious TEAEs considered related (see details below)
5. All TEAEs by maximum severity ('mild', 'moderate', 'severe')
6. TEAEs leading to death
7. TEAEs leading to study discontinuation
8. The TEAEs occurring under infusion and within 24 hours after the start of IMP infusion (Infusion related reaction (IRR))
9. Related TEAEs occurring within 24 hours after start of infusion
10. Adverse events of special interest (AESI):
 - Hypersensitivity/ Anaphylactic reactions/anaphylactic shock: Hypersensitivity (SMQ, restricted to narrow search), Anaphylactic reaction (SMQ, restricted to narrow search), "Anaphylactic shock conditions" (SMQ, restricted to narrow search)
 - Thrombogenicity: SMQ Embolic and thrombotic events (restricted to narrow search)
 - Transmission of infective agents: Preferred Term "Transmission of infectious agent via product" and "Suspected transmission of an infectious agent via product (Preferred Term)
 - Fibrinogen inhibitory antibodies: SOC"Investigations"
11. Related AESI:

- Hypersensitivity/ Anaphylactic reactions/anaphylactic shock: Hypersensitivity (SMQ, restricted to narrow search), Anaphylactic reaction (SMQ, restricted to narrow search), "Anaphylactic shock conditions" (SMQ, restricted to narrow search)
- Thrombogenicity: SMQ Embolic and thrombotic events (restricted to narrow search)
- Transmission of infective agents: Preferred Term "Transmission of infectious agent via product" and "Suspected transmission of an infectious agent via product (Preferred Term)
- Fibrinogen inhibitory antibodies: SOC"Investigations"

Additionally, number and frequencies of patients with TEAEs will be presented by decreasing frequency for all TEAEs, serious TEAEs and TEAEs considered related.

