	In children < 6 years the reconstituted solution of BT524 will be administered intravenously (IV) via an infusion pump with an adapted infusion rate below 5 ml/min (100 mg/minute) according to age, BW, and medical condition at the discretion of the treating physician of the patient.						
	Once valid information on the recovery rate of BT524 is available, the dose to be administered is to be calculated according to the formula given by the Core SmPC:						
	Dose (g) = [d g	esired le /kg) x BV	vels (g/l) – baseline V (kg).	e level (g	g/l)] x	1/recovery (g/l /	
Duration of	Part I: A sir	ngle intra	venous infusion for	the asse	essme	ent of PK/PD.	
Treatment	Part II: On-demand prophylaxis (ODP): Single or repetitive intravenous infusion(s)						
	On-o Sing	demand t	reatment (ODT): etitive intravenous i	nfusion(	s)		
	For each pat least 12 mon	ient the ir th upon e	ndividual treatment enrollment.	period ir	n part	II will last at	

Duration of Follow-up	Part IIndividual follow-up (virus safety) is 49±4 days after the administration of BT524 for PK/PD assessment.Part IIFor each bleeding event, individual follow-up (virus safety) is 49±4 days after the last administration of BT524 for the respective event.
Criteria for Evaluation	
Primary Criterion	
 
Pharmacokinetics (PK)
 
PK parameters will be derived from time concentration profiles using adapted methodology (non-compartmental analysis, compartment analysis, or population modeling, as appropriate/ required).
 
Single-dose PK of fibrinogen antigen will be assessed by the following variables:
 

	
 
Terminal Elimination Half-life (t1/2) for fibrinogen antigen
 
Time to reach Maximum Concentration (tmax)
 
Maximum Concentration (Cmax)
 
Area Under the Concentration-Time Curve (AUC) calculated to the last measured concentration (AUC(0-t)) and extrapolated to infinity (AUC(0-inf)
 
Clearance (CL)
 
Mean Residence Time (MRT)
 
Volume of Distribution (Vss)
 
Incremental Recovery (IVR)
 

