## Safety Visit (Day 49±4):

Visit at the site; also to be performed for each patient prematurely withdrawn from study participation due to any reason.

- Fibrinogen inhibitory antibodies: to be done locally (by available method e.g., correction test of thrombin time)
- Coagulation activation: PT(INR), aPTT, TAT, F1+2, D-dimer, to be done locally or centrally (depending on local availability of validated test systems) ⇒ only in Adults
- Viral safety: collection of retention sample
- IgE: only in case of any suspected hypersensitivity/ allergy/anaphylaxis, to be done centrally
- Vital signs (pulse, blood pressure, body temperature)
- Physical examination

- Adverse events
- Concomitant disease / concomitant medication
- Assessment of risk and burden (paediatric patients)
- 13.1.2 Bleeding Events, Visit Types and Detailed Visit Schedules for On-demand Prophylaxis/On-demand Treatment with BT524 (**PART II**)

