## • Safety Visit:

A *safety visit* is to be conducted on day 49±4 after the (last) administration of BT524 for this bleeding event.

Exception: In case a patient experiences a further bleeding and is to receive at least one administration of BT524 within this time interval of  $49\pm4$  days, the *safety visit* related to the preceding bleeding event can be omitted. In this case, the respective dosing day 0 and the *safety visit* on day  $49\pm4$  after the (last) administration of BT524 related to the current bleeding event will also serve as the safety visit related to the preceding event.

The safety visit is also to be performed for each patient prematurely withdrawn from study participation for any reason.

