Because the study is divided into parts with the possibility of multiple bleeding events in part II, study days are additionally considered for each part II bleeding event separately. More precisely, study day is also defined as the number of days since first dose of study medication of the applicable part II bleeding event and, for a particular date, is calculated as:

$$\text{Study day} = \text{Assessment date} - \text{Date of first dose of study medication for this bleeding event}$$

Due to consideration of several bleeding events as individual cases and the repeated observation periods in part II, related events will be numbered per patient, sorted by start date and time of the events associated with part II participation.

Definition of baseline values

Part I: The baseline value is defined to be the last value, which was assessed during screening before and up to PK dosing Day 0 (all pre-dose). In other words, if for example pre-dose value of fibrinogen antigen at Day 0 of PK is missing, baseline will use the value measured at the screening visit.

Part II: For event-based analysis in part II, baseline value is defined to be Day 0 (pre-dose) per event. In case this is not available, for fibrinogen antigen and fibrinogen activity the baseline values from last event will be used. For all other values Day 0 (pre-dose) will not be replaced, if missing.

Definition of analysis time points or time windows

The following definition of analysis time points, time windows and measurement assignments applies unless specified differently in the respective sections. In particular, for PK parameter specific decisions, the definitions in the PK analyses plans prevail.

Time points for the different endpoints to be measured are specified in the protocol, e.g. in the flowcharts. For each endpoint measurements are taken at an (individual) selection from

time points during Screening, on Day 0 (pre- as well as post-dose) and/or on Days 1, 2, 4, 7, 10, 14 or 49.

Time windows for measuring times are not provided except for the Day 49 measurements, where the window is +/- 4 days. Therefore, no exclusions due to window deviations will be applied. For the PK analysis, actual times will be used. Should time windows be set-up (at a later stage) and result in exclusions of data from analyses, this will be documented in an amendment to this SAP or - at the latest - by means of the applicable data review meeting minutes prior to data base lock.

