6.2 Disposition and withdrawals

The number and relative frequency (i.e. percentages) based on all enrolled patients (APE) will be presented by study part and overall for

- Patients by site and country (worldwide)
- Patients by site and country (European Economic Area (EEA))
- Patients by age group according to EudraCT

(in utero subjects, preterm newborn infants (gestational age <37 weeks), newborns (0-27 days), infants and toddlers (28 days-23 months), children (2-11 years), adolescents (12-17 years), adults (18-64 years), from 65 years on, from 65-84 years, 85 years and over)

The number and relative frequency (i.e. percentages) based on all enrolled patients (APE) will be presented by age group and overall for

Part I:

- Patients participating in part I (Patients enrolled)
- Patients not eligible (Screen failures)
- Patients eligible
- Patients who prematurely discontinued the study part I before treatment (with reasons for discontinuation)

Part II:

- Patients participating in part II (Patients enrolled)
- Patients not eligible (Screen failures)
- Patients eligible
- Patients who prematurely discontinued the study part II before treatment (with reasons for discontinuation)

- Patients who completed the study without bleeding event (study completion defined as regular study completion/no early termination)

The number and relative frequency (i.e. percentages) based on all treated patients (SAF) will be presented by age group and overall for

Part I:

- Patients treated in part I
- Patients who prematurely discontinued the study part I after treatment (with reasons for discontinuation)
- Patients who completed the study part I (Patient was treated in part I and completed/terminated the study after part I PK safety visit; in case PK safety visit was not done/has no date, date is calculated as 49 days after "PK Dosing Day 0".)

Part II:

- Patients treated in part II
- Patients treated in part I and II
- Patients who prematurely discontinued the study part II after treatment (with reasons for discontinuation)
- Patients who completed the study part II (study completion defined as regular study completion/no early termination)

A listing with all the patient disposition data will be also presented.

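### When the Day 49 safety visit is missed, SAP 11.1 counts TEAEs for 49 days from the first infusion of the event, although protocol follow-up runs from the last, so multi-day Part II courses lose the end of their window

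*SAP*

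**What the plan says.** SAP 11.1 limits the TEAE analysis to events "reported from first treatment to the safety visit after treatment (independent of the planned duration between treatment start and Day 49 safety visit"; a further bleeding event before that visit ends the window sooner. If the visit is not done, "the period for inclusion of TEAEs in the analysis is from baseline (treatment start) to 49 days post-baseline". SAP 5.5 leaves no doubt about where that clock starts: for Part II, "study day is also defined as the number of days since first dose of study medication of the applicable part II bleeding event", and the baseline of an event is its Day 0 pre-dose value.

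The protocol counts from the other end of the course. In the Synopsis (Duration of Follow-up, Part II), "individual follow-up (virus safety) is 49±4 days after the last administration of BT524 for the respective event". Protocol 13.1.2.1 and 13.1.2.3 time the safety visit in the same way. So does Table 1 in SAP section 3, and SAP 5.4.2 imputes missing stop dates from the Day 49 visit of the last dose.

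On events outside the window, SAP 11.1 says: "All other TEAEs reported out of these time frames will be counted and listed". Related SAEs are the exception and stay in the analysis whatever their onset.

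**The concern.** The fallback is meant to stand in for a missing visit. That visit is due about 49 days after the last infusion, but the fallback ends 49 days after the first. The two agree only when the event was treated on a single day.

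The plan expects longer courses. Protocol Table 4 foresees maintaining fibrinogen levels in surgical patients until wound healing is complete, and SAP 8.2 tabulates events with 1, 2, 3 and more than 3 infusions. Protocol 11.7 links thrombosis risk particularly to high or repeated dosing. The rule therefore trims follow-up only for the repeatedly dosed events, where late thrombosis is of most interest.

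The stake is the AESI tabulation. Protocol 14.6.1 makes thrombosis an AESI whether serious or not, and SAP 11.1 tabulates AESIs regardless of causality. A thrombosis attributed to surgery and judged unrelated could occur within 49 days of the last infusion and still be missing from that table.

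**Working it through.** **Inputs**
- No-visit window: 49 days from treatment start (SAP 11.1).
- Protocol follow-up: 49 ± 4 days after the last infusion of the event, so the lower limit is 49 − 4 = 45 days (Protocol Synopsis, 13.1.2.1, 13.1.2.3).
- k: days from first to last infusion of one event. The documents give no value, so a range is assumed.
- Part I: one infusion (Protocol 11.1.1), so k = 0.

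The plan states no figure for post-dose coverage under this rule. The only related figure that can be reproduced is the maximum Part I duration: 17 screening days + 49 ± 4 = 66 ± 4 days, as Protocol section 9 states. It confirms that in Part I, where first and last infusion coincide, the 49 days are correctly placed.

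**Formulas**
- Days covered after the last infusion = 49 − k.
- Shortfall against 49 days = k.
- Shortfall against the 45-day lower limit = max(0, k − 4).

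| k (assumed) | Days covered after last infusion | Short of 49 | Short of 45 |
|---|---|---|---|
| 0 | 49 | 0 | 0 |
| 4 | 45 | 4 | 0 |
| 5 | 44 | 5 | 1 |
| 7 | 42 | 7 | 3 |
| 14 | 35 | 14 | 10 |
| 21 | 28 | 21 | 17 |

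As a share of the 49 days, k = 7 loses 7/49 = 14% and k = 14 loses 14/49 = 29%. If the fallback ran from the last infusion, coverage would be 49 days for every k.

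**Conditions for a loss.** All must hold: a Part II event, infusions on more than one day, the safety visit not done, and no further treated event opening a new window before the lost days.

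**What is lost.** An event in the last k of the 49 post-dose days is treated as follows under SAP 11.1:
- related and serious: kept in the analysis;
- unrelated and serious: counted and listed, not in the SOC/PT or AESI incidence tables;
- non-serious, related or not: the same.

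**Scale of one omission.** With about 36 patients planned for Part II, one patient left out of an AESI row changes it by 1/36 = 2.8 percentage points.

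**The case against.** The strongest reply is that the gap is narrow. It needs every condition above, and because the protocol itself allows ± 4 days, a course spanning up to 4 days still leaves at least 45 post-dose days. This stands and limits the size of the point. It does not explain why the SAP counts from the first infusion when the protocol and its own Table 1 count from the last.

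It can also be said that few events would be known in the lost days when nobody attended a visit. That is fair. But Protocol 14.6.2 records all TEAEs up to the respective 49-day visit. Where no such visit closed the period, an event learned of later can be in the database, and only the SAP rule would remove it.

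Three stronger readings are tempting, and the documents do not support them.

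- *An early visit at withdrawal wrongly cuts the window.* Protocol 13.1.2.3 says "The safety visit is also to be performed for each patient prematurely withdrawn from study participation for any reason", and SAP 11.1 ends the window at the visit, so a reader might infer that a patient seen on day 7 loses 42 of 49 days. But under Protocol 14.6.2 and 14.6.2.1 only related serious TEAEs are recorded after the last 49-day visit, and SAP 11.1 already keeps related SAEs. If the withdrawal visit serves as that visit, the loss is mostly nominal window, not collected events. The extra follow-up visits in Protocol 14.6.2.1 concern AEs or laboratory abnormalities already present at the last visit, so they are not a source of new excluded events.
- *Late events disappear from the report.* They do not. They are counted and listed, and the overview on all enrolled patients has rows for any AE, any SAE and any death that are not limited to TEAEs.
- *Withdrawn patients will be reported as Part I completers.* SAP 6.2 defines a completer thus: "Patient was treated in part I and completed/terminated the study after part I PK safety visit". It does not require the visit to fall at Day 49 ± 4, so a patient withdrawn with an early visit could fit both this row and the row for premature discontinuation. But the safety visit is held for patients already withdrawn, so whether termination comes after it depends on how the dates are read. This is an ambiguity in SAP 6.2, separate from the TEAE window.

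**Conclusion.** The no-visit rule in SAP 11.1 is inconsistent with the protocol and with SAP Table 1, and should be corrected. It shortens post-dose coverage by k days, to 42 days for a 7-day span and 35 for a 14-day span, and below the protocol's lower limit from k = 5. The course lengths are assumed, and neither the number of missed visits nor the number of events in the lost days is known. The documents therefore show that incidence could be understated for some repeatedly dosed Part II events, not that it is. Part I and events with a visit held are unaffected.

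The completer wording in SAP 6.2 is secondary. One patient classified the wrong way would move Part I completion by 1/23 = 4.3 percentage points, and through SAP 4.1.2.1 could enter the enrolled set for Part II. That patient would not enter the Part II safety set, which requires exposure in Part II.

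**What to change.** In SAP 11.1, replace the no-visit window with: *from treatment start to 49 days after the last BT524 infusion of that event, or to the start of the next treated event if earlier.* Leave the window as it is when the visit was held. Extending it past an on-time visit on Day 45 to 48 would add days in which, after the last such visit, only related serious events are recorded, and so mix full and partial collection in one table.

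As a lower priority, define Part I completion in SAP 6.2 as no early termination, matching the Part II definition in the same section, so that no patient can be counted as both discontinued and completed.

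The cost is one derived date in the programs and the SAP wording. No new data are needed, and TEAE counts may rise slightly.

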### 14.5.2 Methods for Assessing, Recording and Analyzing Safety Parameter(s)

All laboratory results have to be evaluated in the eCRF according to the following pattern:

- a) outside reference range but not clinically relevant (e.g. due to already known conditions, due to sampling conditions, only marginal deviation, due to underlying diseases in the study population)
- b) outside reference range and clinically relevant.

Laboratory values which are outside the reference range and assessed as clinically relevant have to be controlled and documented as adverse events if they occur for the first time after administration of investigational medicinal product BT524.

If abnormal laboratory values are signs of an adverse event (e.g. an infection) that has already been reported during the present study, this has to be stated but the respective abnormal laboratory value does not constitute a separate adverse event.

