## Adverse Event of Special Interest (AESI)

An AE of special interest (serious or non-serious) is one of scientific and medical concern specific to the sponsor's IMP or development program, for which ongoing monitoring and immediate communication by the investigator to the sponsor may be appropriate. Such events may require further investigation in order to characterize and understand them. Reporting / Notifying requirements are detailed in section 14.6.4.

The following AEs have been defined as AESI for this study: Thrombosis or TEE, and suspicion of transmission of infective agents (viral safety).

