### Period:

• Patient Enrolment to the First Administration of Study Drug: Non-treatment emergent AEs will be recorded from the time when the patient is enrolled into the study (date of signature of the informed consent) until first administration of study drug.

- After Administration of Study Drug until respective 49 day visit (Part I and Part II): All TEAEs will be recorded.
- **In-between individual 49 day periods or after last 49 day visit:** Any serious treatment emergent AE considered to be related to the study medication by the investigator will be recorded.

If an AE (serious or not) started after administration of study drug but did not end before the 49 day visit, the investigator should make a reasonable effort to establish the outcome and the end date. If this is not possible, the outcome recorded at the 49 day visit will be assumed to be the final outcome.

If an event stops and later restarts, all the occurrences must be reported. AEs assessed as related to study medication by the investigator and all SAEs must be followed up until resolution.

The investigator should attempt to establish a diagnosis of the event based on signs, symptoms and/or other clinical information. In such cases, the diagnosis should be documented as the AE and/or SAE and not the individual signs/symptoms. Signs/ symptoms should be documented only if a diagnosis cannot be established. If a diagnosis is accompanied by unusual symptoms, the diagnosis itself and the symptoms have to be reported separately.

In addition to the definition as given, the following special types of events should be recorded:

Laboratory values that are outside the normal range and if, in the opinion of the investigator, these values represent a clinically relevant change versus pre-treatment values are also defined as AEs.
 If abnormal laboratory values are signs of an AE (e.g. an infection) that has

If abnormal laboratory values are signs of an AE (e.g. an infection) that has already been recorded, the respective abnormal laboratory value does not constitute a separate AE. Wherever reasonable the reporting investigator will use the clinical term rather than the laboratory term (e.g., anemia versus low hemoglobin value).

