### 14.6.4 Notifying of Adverse Events

### 14.6.4.1 Responsibilities of Investigator

In this study AEs will be reported electronically from the site to the sponsor using the eCRF.

All known information regarding IRAEs (SAEs, AESIs, pregnancy, and AEs leading to withdrawal) must be recorded on the AE log of the eCRF **within 24 hours** of the site learning of the event (see also section 14.6.2.1).

In case the electronic system is not function 24 hours, SAE paper forms will be provided to be used in the case of an IRAE. The paper forms will also need to be faxed or e-mailed to the sponsor within 24 hours of the site learning of the AE.

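### A suspected viral transmission recorded only under the infection's name could be missing from the SAP's AESI tables, because that category is selected by two Preferred Terms alone

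*SAP*

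**What the plan says.** Protocol 14.6.1 names the study's AESIs as "Thrombosis or TEE, and suspicion of transmission of infective agents (viral safety"). AESIs are immediately reportable. For recording, protocol 14.6.2 asks the investigator to establish a diagnosis where possible: "In such cases, the diagnosis should be documented as the AE and/or SAE and not the individual signs/symptoms".

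SAP 11.1 codes adverse events in MedDRA. Items 10 (AESI) and 11 (related AESI) then identify the transmission category by two Preferred Terms, with the same wording in both items: "Transmission of infectious agent via product" and "Suspected transmission of an infectious agent via product (Preferred Term"). Nothing else is given for this category. There is no grouped search, no list of infections, no use of the investigator's own AESI report and no medical review of candidate cases. Appendix 15.1 of the SAP lists the resulting tables as 14.3.2.13.1 to .4 and 14.3.2.17.1 to .4.

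**The concern.** The protocol's AESI is a clinical judgement about where an infection came from. The SAP's rule is a match on two coded terms. The two agree only if the suspicion itself is what the site enters as the event. If the site enters the infection, the event may be coded to that infection and the search will not find it, even when the site reported it as an AESI within 24 hours.

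BT524 is made from human plasma, and viral safety is one of the two AESIs that the protocol defines. The AESI tables are also the only dedicated summary of possible transmission after dosing: SAP 11.7 tabulates the part I pre-dose viral results and only lists the retention samples taken at the safety visits. A zero in the AESI tables could then reflect the search terms and not the absence of a suspected case.

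**Working it through.** The documents state no figure for this point, so the check compares the definition with the selection rule and then counts tables.

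**From event to table**

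1. *Entry.* Besides the diagnosis rule, protocol 14.6.2 prefers the clinical term over the laboratory term where reasonable. Protocol 14.5.2 uses an infection as its example of an event in its own right: "If abnormal laboratory values are signs of an adverse event (e.g. an infection"). Under protocol 14.6.4.1, AESI information "must be recorded on the AE log of the eCRF" within 24 hours. Neither document describes an AESI field in the eCRF, or tells sites to enter the suspicion of transmission as the event or as a second event.
2. *Coding.* SAP 11.1 presents events by System Organ Class and Preferred Term. I assume that an event entered under a disease name is coded to that disease. The coding conventions are not in these documents.
3. *Selection.* An event coded to a disease name matches neither Preferred Term. By contrast, thrombosis in the same items is found by a grouped search: "Thrombogenicity: SMQ Embolic and thrombotic events (restricted to narrow search").

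**Tables that carry the rule (SAP Appendix 15.1)**

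| Population | All TEAEs | Related TEAEs |
|---|---|---|
| SAF I and II, overview | 14.3.2.13.1 | 14.3.2.17.1 |
| SAF I and II, by age group | 14.3.2.13.2 | 14.3.2.17.2 |
| SAF I | 14.3.2.13.3 | 14.3.2.17.3 |
| SAF II | 14.3.2.13.4 | 14.3.2.17.4 |

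Total: 4 + 4 = 8.

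**Tables wrong for one missed case in one study part, onset inside the analysis window**

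- Rated not related: the two combined tables plus the table for that part, 2 + 1 = 3 of 8.
- Rated related: the same three in each series, 3 + 3 = 6 of 8.
- All 8 are wrong only if related cases are missed in both parts.

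**Size of one case**

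- Planned total of about 36 patients (protocol 12.1): 1/36 = 2.8%, shown as 0%.
- Part I, planned 23 patients (SAP section 3, Table 1): 1/23 = 4.3%, shown as 0%.

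**The case against.** The strongest reply is that the gap may never open. The second Preferred Term closely mirrors the protocol's wording, so a site reporting this AESI could well enter the suspicion itself, and the search would then find it. The diagnosis rule in protocol 14.6.2 is about diagnosis versus signs and symptoms. It does not say how to record a suspicion of transmission and does not forbid entering one. The laboratory route is also narrow: scheduled viral analysis is pre-dose, and later serum is stored for possible testing (protocol 14.5.1.10), so a positive post-dose result would mostly come from testing done because suspicion already existed.

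Nor would the event disappear. It would be in Listing 16.9.1. Within the analysis window it would appear by name in the all-TEAE tables, in the related-TEAE tables if rated related, and in the serious tables if serious. Related serious events are analysed whatever their onset (SAP 11.1). In a study of about 36 patients, an attentive reader would probably see it.

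All of this stands, and it limits the point to a conditional one. What remains is that neither document requires the entry on which the search depends, and no second route brings a reported AESI into its own tables.

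A broad term list has its own problem. Part II lasts at least 12 months and includes children, so counting every listed infection after the first dose would go beyond the protocol's definition. Hits from a list therefore need review before they count.

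**Conclusion.** The selection rule is narrower than the AESI it is meant to summarise. A suspected case entered only by the infection's name could be left out of up to 6 of the 8 AESI tables if related, or 3 if not, turning 2.8% overall (4.3% in part I) into 0%. Protocol 14.6.1 rates an event as related when a reasonably possible link to the study drug cannot be excluded, so a suspected transmission would usually fall in the 6-table case.

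This rests on three assumptions: such a case occurs, it is entered only under the disease name and coded accordingly, and the planned patient numbers serve as denominators. Whether the two strings are valid Preferred Terms in the MedDRA version used cannot be checked from the documents.

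A reader might infer that such infections will be counted as zero in all eight tables, or that they will be lost from the report. The documents support neither. Entry under the suspicion term is open to sites, one case cannot affect all eight tables, and the listings and general TEAE tables still carry the event. Nor do the documents show that any case was missed. This is a gap in one safety category, worth closing before lock. It does not touch the pharmacokinetic or efficacy analyses.

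**What to change.** In SAP 11.1, items 10 and 11, define the transmission category as the union of:

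- (a) adverse events reported as this AESI, identified by reconciling the AE data with the immediately reportable events that protocol 14.6.2.2 places in the sponsor's safety database;
- (b) the two Preferred Terms already named;
- (c) events found by a written term list for HIV, HBV, HCV, HAV and parvovirus B19 infection or positive test, with onset after the first BT524 dose, counted only if a documented medical review before database lock judges product transmission to be suspected.

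Item 11 keeps its restriction to related events. Footnote the source (a, b or c) of each counted case, and list the cases that were reviewed and not counted.

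The cost is a short text change, a term list, one reconciliation and a brief review, with no new data. Two limits should be stated. The reconciliation assumes that the safety database shows which reportable events were reported as this AESI, because no dedicated eCRF field is described. The term list would also be written after the data review of 25 June 2020 in an open-label study, so its date and that fact should be disclosed.
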